6.3 Potential Benefits to the Patient

The potential benefits of the EndoRotor® device are as follows:

- May result in less time to resolution of WOPN
- Complete removal of necrotic debris requiring less treatments

7.0 STATISTICAL METHODS

7.1 General Principles

While this protocol does specify primary and safety endpoints, these are not meant to define subject and study success. Instead, the results of this evaluation will be used to establish the safety and efficacy profile of the EndoRotor Procedure and to evaluate the effect size for powering future clinical investigations.

Nominal and ordinal variables for each time period will be presented using frequencies and percent of patients in each category. Interval and ratio variables for each time period will be presented using means and standard deviations, median, quartiles, and minimum and maximum. For variables collected at multiple follow-up time periods, tables, which include change from baseline, will be presented at each follow-up visit.

Distributions of each continuous variable will be assessed prior to analysis and examined for normality. Data with interval or ratio scales to be analyzed that are not normally distributed will be analyzed using non-parametric statistics. Statistical tests will be performed using two-sided significance levels of 5% unless otherwise specified.

7.2 Analysis Populations

Study Population: The study population includes all subjects consented at the site. Within this population there are Screened, Safety and Treated populations.

Screened: This population includes all subjects that meet the inclusion and exclusion criteria as specified in the protocol.

Safety: This population includes all subjects in whom the EndoRotor procedure was attempted. Subjects will be analyzed according to the treatment received.

Treated: This population includes all subjects that successfully received the EndoRotor debridement procedure.

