Clinical Sites:	Up to 6 in the United States and 4 in the EU will enroll subjects.
Enrollment:	The sites will enroll a total of 30 subjects, 15 minimum from the US that meet all inclusion and exclusion criteria.

Inclusion Criteria:	
 1. Subjects who are ≥ 22; inclusive of males and females. 2. Patients with symptomatic pancreatic necrosis due to acute pancreatitis that have an indication to undergo endoscopic necrosectomy after having undergone EUS-guided drainage 3. Imaging suggestive of greater than or equal to 30% necrotic material 4. Walled off pancreatic necrosis size ≥ 6 cm and ≤ 22cm 5. Subject can tolerate repeated endoscopic procedures 6. Subject capable of giving informed consent. 7. Subjects with the ability to understand the requirements of the study, who have provided written informed consent, and who are willing and able to return for the required follow-up assessments through 21 (+/- 7) days, as indicated.
Exclusion Criteria:	
 1. Subject unable to give informed consent. 2. Subject is unwilling to return for repeated endoscopies. 3. Documented Pseudoaneurysm > 1cm within the WOPN 4. Intervening gastric varices or unavoidable blood vessels within the access tract (visible using endoscopy or endoscopic ultrasound). 5. Dual antiplatelet therapy or therapeutic anticoagulation that cannot be withheld for the procedure 6. Any condition that in the opinion of the investigator would create an unsafe clinical situation that would not allow the patient to safely undergo an endoscopic procedure (lack of medical clearance). 7. Pregnant or lactating women or women of childbearing potential who do not employ a reliable method of contraception as judged by the Investigator, and/or are not willing to use reliable contraception for the duration of study participation. 8. Patient is known to be currently enrolled in another investigational trial that could interfere with the endpoint analyses of this trial.
Primary Analysis:	Subjects enrolled in the study and who met all I/E criteria and are treated with the EndoRotor Device.
Study Device:	Interscope EndoRotor® Resection System

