4.9 Subject Screening

Following placement of stent and determination of need for necrosectomy study eligibility is confirmed and the patient will receive the EndoRotor® intervention. The patient will be enrolled upon insertion of the catheter into the endoscope. Screening shall include:

- Pregnancy test – within 1 day of the procedure.
- Medical clearance in advance of the procedure.
- WOPN resulting from necrotizing pancreatitis per high resolution vascular CT with the characteristics per the 2012 Revised Atlanta Classification.
- Imaging suggestive of greater than 30% necrotic material
- WOPN size ≥ 6 cm and ≤ 22 cm

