4.14 Study Withdrawal & Lost to Follow Up

Study participation is voluntary and subjects may withdraw their consent at any time. **ALL** enrolled subjects and their status in the study will be included in the study reports.

- **Treated and Study Criteria Not Met:** Subjects who are enrolled and treated, but who are later discovered to not meet all of the study criteria, will remain in the study and complete all of the study testing and follow-up requirements. A protocol deviation will be completed for study subjects who are

found to be ineligible after enrollment. These subjects may be excluded from the Per Protocol analysis depending upon the nature of the protocol deviation.

- **Patient Withdrawal:** Participation in any clinical investigation is voluntary and a patient is allowed to discontinue their participation at any time. Subjects may withdraw at their own discretion with or without reason and without any impact on their continued medical care. If a patient voluntarily withdraws from the study, no additional medical data will be collected, and the patient will not continue in the study.
- Subjects who withdraw from the study will not be replaced; however, if a patient withdraws their consent **BEFORE** being treated with the study device (before insertion of the catheter into the endoscope), and/or before the 21 (+/-7) day follow-up, he or she will not be included in the analysis.
- **Investigator Termination:** The site Investigator may terminate the patient’s procedure if it is in the patient’s best interest not to continue; however, the patient is withdrawn from the study and will not be included in the analysis.
- **Lost-to-Follow-up:** A patient who does not complete follow-up requirements and does not officially withdraw from the study is considered lost-to-follow-up. This does not apply to missed visits where the patient misses one of the follow-up contact time points but completes the subsequent one. In order to consider a patient lost-to-follow-up, site personnel should make all reasonable efforts to locate and communicate with the patient. All attempts to contact the patient must be recorded in the study notes, including the date, time, and name of site personnel who have attempted to contact the patient.

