7.4.2 Safety Analysis

All safety data will be displayed and analyzed using descriptive statistical methods. No formal inferential analysis is planned for safety comparisons. The safety endpoint is the absence of any device or procedure related serious significant adverse events (SAEs) within the 21 (+/-7) days following EndoRotor procedure. These will be presented overall and by system organ class and preferred term (PT). This will be conducted on the Safety analysis set overall. Subjects who experience more than one event in a given System Organ Class (SOC) and PT will be counted once within that SOC and PT. The total number of events and the number and percentage of subjects with each event will be reported.

Adverse Events: AEs, SAEs and UADEs will be coded using MedDRA. Treatment Emergent AEs, SAEs and UADEs are defined as events starting or worsening after start of the procedure. The number and percent of patients with Treatment Emergent AEs, SAEs and UADEs will be summarized overall and by primary SOC and preferred term (PT). Subjects who experience more than one event in a given SOC and PT will be counted once within that SOC and PT.

The number and percent of subjects with treatment emergent AEs, UADEs and SAEs will be further presented by severity and by relationship to the device or procedure. In tabulating the severity of AEs on a per subject basis, the greatest severity will be assigned to a subject should there be more than one occurrence of the same AE with different reported severities. Relationship will be categorized as unrelated, possibly, probably and definitely related. The highest level of association will be reported for subjects with different relationships for the same AE.

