7.4.3 Effectiveness Analysis

Effectiveness Analysis will be assessed via the following secondary endpoints:

- Successful clearance of necrosis in the collection being treated during direct endoscopic necrosectomy where success is defined as at least 70% of the necrotic debris in the WOPN cavity is removed based on CT evaluation of the cavity at 21 (+/-7) day follow up visit.
- Assessment of total procedure time to achieve clearance of necrosis for all procedures
- Assessment of adequacy of debridement
- Assessment of total number of procedures to achieve clearance of necrosis
- Assessment of length of hospital stay and utilization
- SF-36 Questionnaire

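### Section 7.2 admits subjects to the Treated set by an undefined success, and 7.4.3 names no set, so the clearance rate could lose failed or aborted cases from its denominator

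*Combined protocol and SAP*

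**What the plan says.** Section 4.9 ties enrolment to a physical event: "The patient will be enrolled upon insertion of the catheter into the endoscope". Section 4.14 uses the same event when it deals with consent withdrawn before "being treated with the study device (before insertion of the catheter into the endoscope").

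Section 7.2 then defines two sets that concern us. One is broad: "Safety: This population includes all subjects in whom the EndoRotor procedure was attempted". The other is narrower: "Treated: This population includes all subjects that successfully received the EndoRotor debridement procedure". Neither 7.2 nor Appendix 2 says what makes receipt successful.

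On use of the sets, 7.4.2 says of the safety endpoint: "This will be conducted on the Safety analysis set overall". Section 7.4.3 opens with "Effectiveness Analysis will be assessed via the following secondary endpoints" and lists the endpoints, including clearance (70% or more of the debris gone on CT at follow-up), but gives no population. The Protocol Summary's Primary Analysis line reads: "Subjects enrolled in the study and who met all I/E criteria and are treated with the EndoRotor Device".

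Two further rules affect the denominator. Under 4.14, if the investigator terminates a procedure, "the patient is withdrawn from the study and will not be included in the analysis"; the same section also leaves out subjects who withdraw consent before follow-up. Section 7.5 rules out imputation and uses available data only.

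**The concern.** A subject whose catheter was inserted but whose debridement could not be carried through (for example because of device failure or debris out of reach) has been enrolled under 4.9 and is past the treatment point used in 4.14. Under 7.2 the same subject may not be Treated. Because the Safety set already covers attempts, the extra word in the Treated definition has to remove some attempted cases, and it does so on a result of the intervention.

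In a single-arm trial no control rate would shift in the same way. Section 7.1 intends the results to inform the effect size for later studies, and 4.7 relies on the data for the benefit-risk profile. A clearance rate computed only where the procedure worked would carry an upward bias into both uses.

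**Working it through.** **No plan figure to reproduce.** Section 7.3 states that the 30 subjects were not chosen on statistical grounds, and no clearance or technical-failure rate is assumed anywhere. The check is therefore a comparison of definitions followed by denominator arithmetic.

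**Step 1: which set serves which analysis.**
- Safety endpoint: the Safety set (7.4.2).
- Effectiveness endpoints: no set named (7.4.3).
- Treated set: defined in 7.2, with no analysis expressly assigned to it.

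The exposure is therefore the effectiveness analysis, and it is conditional on the analyst choosing Treated.

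**Step 2: inputs.**
- N = 30 subjects (7.3).
- x = subjects cleared: assumed 24, with 18 and 21 as alternatives.
- k = subjects dropped by the success condition: assumed 1 to 3.
- c = cleared subjects among those dropped: assumed 0.

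**Step 3: formula.** The rate on all subjects with catheter entry is x/30. The rate on the 7.2 Treated set is (x − c)/(30 − k). With c = 0:

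| Cleared (x) | x/30 | k = 1 (x/29) | k = 2 (x/28) | k = 3 (x/27) |
|---|---|---|---|---|
| 18 | 60.0% | 62.1% | 64.3% | 66.7% |
| 21 | 70.0% | 72.4% | 75.0% | 77.8% |
| 24 | 80.0% | 82.8% | 85.7% | 88.9% |

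The rise is 2.1 to 2.8 points for one dropped subject and 6.7 to 8.9 points for three. With x = 24, the exact (Clopper-Pearson) 95% interval moves from 61.4–92.3% on 24/30 to 70.8–97.6% on 24/27.

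**Step 4: direction.** (x − c)/(30 − k) exceeds x/30 exactly when c/k < x/30, that is, when the dropped subjects clear less often than the whole group. With x = 24 and k = 3, c = 0, 1, 2, 3 gives 24/27 = 88.9%, 23/27 = 85.2%, 22/27 = 81.5% and 21/27 = 77.8%. The rate falls only if all three dropped subjects cleared, which is unlikely for cases dropped because the procedure failed.

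**Step 5: would deleting the word be enough?** No. An investigator-terminated case is still removed by 4.14. A failed case without a follow-up CT is still removed by the available-data rule in 7.5. The denominator returns to 30 only if these subjects are kept and given an outcome.

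**The case against.** The strongest reply is that 7.2 deliberately pairs an attempted set with a received set, that the remark in 4.14 only fixes when a consent withdrawal counts as preceding treatment, and that no planned rate is tied to Treated. Much of this stands. The 4.14 parenthesis is not a population definition, so this is an inconsistency of usage rather than two rival definitions of one set. It also stands that the use of Treated for clearance is not stated. But with no set named in 7.4.3, nothing prevents that choice after the data are seen.

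It is also fair that success may mean no more than technical delivery, and that Treated is defined by subject with up to four procedures each, so one failed procedure need not remove anyone. A reader might infer that the set selects on the 70% clearance endpoint itself. The text does not establish that. What holds under either reading is that membership is settled by a result after enrolment.

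A reader might further infer that the primary safety result is flattered. The documents do not support this: 7.4.2 puts the safety endpoint on the attempted set, where failed procedures remain. Nor can the Summary's Primary Analysis line be equated with the 7.2 Treated set. It carries no success condition and adds an eligibility condition that Treated lacks; the link is only a shared word.

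Finally, 4.14 requires all enrolled subjects and their status to be reported, so exclusions would be visible, and 7.1 says the endpoints do not define study success. This limits the harm but does not correct the rate.

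**Conclusion.** The point holds for effectiveness, conditionally. The Treated set depends on an undefined post-enrolment result, and the clearance endpoint has no named set. If Treated is used, clearance is overstated by about 3 to 9 points at 24 of 30 cleared (80.0% to between 82.8% and 88.9%). That rests on the assumptions that 1 to 3 subjects are dropped and that none of them cleared; neither number comes from the documents. The largest of these shifts, 8.9 points, is well inside the sampling uncertainty of 30 subjects (the interval on 24/30 spans 30.9 points), but it is systematic and avoidable. The Treated definition does not affect the safety endpoint. The 4.14 rule on terminated procedures is a separate matter: as written it also sits awkwardly with a Safety set of all attempts.

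**What to change.** - In 7.2, define Treated as every subject in whom the EndoRotor catheter entered the endoscope, and delete the success condition.
- In 7.4.3, name this set for the clearance endpoint. State that failed or aborted cases count as not cleared, including those without a follow-up CT. Write the rule per subject, so that it covers someone with an aborted procedure followed by a completed one.
- Reconcile the 4.14 analysis exclusions (investigator-terminated procedures and withdrawal before follow-up) and the Summary's Primary Analysis line, including its eligibility condition, with 7.2 and 7.4.2.
- Report procedural failures as a separate count with reasons.

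The cost is wording in the protocol and SAP. Treated becomes nearly the same set as Safety, and the clearance figure may be slightly less favourable. The change should be made before outcome data are reviewed.

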7.3 Sample Size

This study will enroll a total of 30 subjects. Sample size determination is based on the nature and objective of this study and not statistical considerations. The data will be sufficient to provide an assessment of the safety profile of the EndoRotor for DEN in WOPN as well as provide initial efficacy data to support an evaluation of the benefit/risk profile.

7.4 Statistical Analysis

7.4.1 Demographic and Baseline Characteristics

Demographic and baseline data will be summarized using summary statistics of sample size, mean, standard deviation, median, quartiles, min and max for continuous variables and proportions and frequency of patients for categorical values. Demographics will be presented for the following analysis populations:

7.4.2 Safety Analysis

All safety data will be displayed and analyzed using descriptive statistical methods. No formal inferential analysis is planned for safety comparisons. The safety endpoint is the absence of any device or procedure related serious significant adverse events (SAEs) within the 21 (+/-7) days following EndoRotor procedure. These will be presented overall and by system organ class and preferred term (PT). This will be conducted on the Safety analysis set overall. Subjects who experience more than one event in a given System Organ Class (SOC) and PT will be counted once within that SOC and PT. The total number of events and the number and percentage of subjects with each event will be reported.

Adverse Events: AEs, SAEs and UADEs will be coded using MedDRA. Treatment Emergent AEs, SAEs and UADEs are defined as events starting or worsening after start of the procedure. The number and percent of patients with Treatment Emergent AEs, SAEs and UADEs will be summarized overall and by primary SOC and preferred term (PT). Subjects who experience more than one event in a given SOC and PT will be counted once within that SOC and PT.

The number and percent of subjects with treatment emergent AEs, UADEs and SAEs will be further presented by severity and by relationship to the device or procedure. In tabulating the severity of AEs on a per subject basis, the greatest severity will be assigned to a subject should there be more than one occurrence of the same AE with different reported severities. Relationship will be categorized as unrelated, possibly, probably and definitely related. The highest level of association will be reported for subjects with different relationships for the same AE.

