4.2 Overview of Study Design

A prospective, single arm, open label, multi-center, trial to evaluate the safety and effectiveness of the Interscope EndoRotor® Resection System in subjects requiring direct endoscopic necrosectomy with walled off pancreatic necrosis (WOPN). Total enrollment of 30 subjects with at least 15 enrolled in the US.

Subjects will be debrided with the EndoRotor at least 2 days following initial stent placement with a maximum of 4 EndoRotor procedures. A minimum of 2 days is required between each EndoRotor procedure and all procedures need to be completed within a 14 (+7/-0) day period. Follow up is completed to 21 (+/-7) days after first EndoRotor debridement procedure.

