4.3 Primary Endpoint

The primary endpoint of this study is the freedom from major complications. The safety endpoint will include an assessment of the safety of the EndoRotor when performing endoscopic necrosectomy. For the purpose of this study, the safety evaluation shall include complications associated with endoscopic necrosectomy through the 21 (+/-7) day follow-up period. Potential endoscopic complications include perforation and bleeding.

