5.4.2 Follow-up Visit 21 Days (± 7 days)

All subjects will return to the clinic for the 21 (+/-7) day visit as determined from the last EndoRotor procedure. Results of the following study procedures will be recorded in the subject's source medical record and on the appropriate CRF:

- CT Scan Imaging: Record results and the percent resolution of necrotic debris in the collection being treated
- Surveillance endoscopy (only if clinically required) whereby physician can use local standard of care to continue to treat the patient if required
- Physical Exam
- SF-36 Questionnaire

All subjects will exit from the study after this visit; however, all subjects should be followed according to the Investigator's clinical standard practice guidelines for safety.

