10.5 Reporting of Adverse Events

All adverse events, including SAE’s and UADE’s, will be monitored from the time of enrollment through the

study exit. A description of the event, including the start date, resolution date, action taken, and the outcome shall be provided, along with the Investigator's assessment of the relationship between the AE and the study device and procedure.

All AE's should be followed until the event is resolved or judged to be clinically stable. The clinical site should plan to provide additional, relevant AE follow-up information to the Sponsor upon request.

All SAEs, DRSAEs, and UADE's must be reported to the Sponsor and/or CRO and the primary Investigator at the site **within 24 hours** of the Investigator becoming aware of the event. Additionally, the Investigator should notify their IRB, and local/national authorities as required, within their specified timeframes. The Sponsor and CRO will decide whether all of the local Investigators need to be informed immediately, or whether this can be postponed until the next regularly scheduled study update.

A completed SAE CRF **must** be uploaded to the Sponsor's secure web server **within 7 days of the event**. The minimum required data to be recorded for an SAE includes: date of event, type of event, duration of event, severity, seriousness, action taken, outcome, causality and relationship to the Interscope device and procedure. In the case of a DRSAE, whenever possible, the device involved in the failure or malfunction is to be returned to Interscope for analysis.

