APPENDIX 1 – SCHEDULE OF STUDY ASSESSMENTS

A schedule of study assessments is provided below.

	Baseline	Index Procedure (Day 0)²	Procedures 2 through 4 14 (+7/-0) Days³	Discharge	21 (±7) Days⁴
Confirm Eligibility	X	X			
Informed Consent	X				
Demographics	X				
Medical History	X				
Physical Examination	X				X
SF-36	X				X
Pregnancy Test ¹	X				
EndoRotor® Procedure		X	X		
CT Imaging (Standard of Care)	X				X
Adverse Event Assessment		X	X	X	X

¹ Urine pregnancy test for female of child bearing potential within 1 day of procedure.

² The index procedure must be done within 2 weeks of enrollment with outpatient video documentation of before and final results from procedure.

³ Procedures 2 through 4 at 14 (+7/-0) days is not required if there is at least 70% removal of accessible necrotic debris in the collection being treated.

⁴ Visit based on 21 (+/-7) days from last EndoRotor procedure

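### The primary safety endpoint uses the 21 (±7) day visit tolerance as its time limit, so compliant subjects are observed for 14 to 28 days after the last procedure and the reported percentage has no single time horizon.

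*Combined protocol and SAP*

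**What the plan says.** Section 4.3 makes freedom from major complications the primary endpoint and assesses "complications associated with endoscopic necrosectomy through the 21 (+/-7) day follow-up period". Section 7.4.2 restates the safety endpoint as absence of device- or procedure-related SAEs "within the 21 (+/-7) days following EndoRotor procedure". It reports numbers and percentages of subjects, descriptively, and provides no person-time rate or time-to-event estimate. Section 7.5 rules out imputation.

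The end of observation is set in two places. Section 5.4.2 says "All subjects will exit from the study after this visit", with later care left to the investigator's usual practice. Section 10.5 says that adverse events "will be monitored from the time of enrollment through the" study exit.

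The timing of the visit is stated inconsistently:
- 5.4.2: "All subjects will return to the clinic for the 21 (+/-7) day visit as determined from the last EndoRotor procedure".
- Appendix 1, footnote 4: "Visit based on 21 (+/-7) days from last EndoRotor procedure". The Protocol Summary also counts from the last procedure.
- 4.2: "Follow up is completed to 21 (+/-7) days after first EndoRotor debridement procedure".
- 7.4.2 does not say which procedure it means.

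Collection starts at the index procedure, because under 4.9 "The patient will be enrolled upon insertion of the catheter into the endoscope".

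**The concern.** A ±7 day tolerance is ordinary for scheduling a measurement. Here the same tolerance also limits the endpoint and ends adverse event ascertainment. Take two subjects who each have a first related SAE 18 days after their last procedure. The one seen on day 14 has already left the study and is recorded as event-free. The one seen on day 28 is recorded as having an event. Both followed the protocol exactly, and only the appointment date differs.

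Safety is the main purpose of the trial. Section 4.7 relies on the data for the benefit-risk profile, and 7.1 intends to use the results to power later studies. With no formal test, the percentage itself is the result. A percentage that mixes 14-day and 28-day observation cannot be labelled as a risk by any particular day, or compared cleanly with a figure that can.

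**Working it through.** **Is there a common cut-off anywhere?** Sections 4.3, 5.4.2, 7.4.2, 7.5, 10.5 and Appendix 1 give none. Three provisions might seem to supply one:
- 10.5 follows adverse events to resolution or stability. That covers events already begun, not new onsets after exit.
- 5.4.2 mentions follow-up after exit, but under usual practice and with no study data collection specified.
- 5.4.3 records unscheduled visits and calls. It does not extend monitoring past the exit at which 10.5 ends it.

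**Length of observation after the last procedure** (5.4.2, Appendix 1)
- Shortest: 21 − 7 = 14 days. Longest: 21 + 7 = 28 days. Ratio: 28/14 = 2.0.

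**Length of observation from the index procedure** (4.9, 10.5; treatment period up to 14 + 7 = 21 days, 4.2)
- Shortest: 0 + 14 = 14 days. Longest: 21 + 28 = 49 days. Ratio: 49/14 = 3.5. Part of this spread reflects different lengths of treatment, not the visit window.

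**Effect on the observed risk.** The plan has no event rate to reproduce, so the rates below are assumptions. Let p be the risk by day 21.
- Constant hazard: risk(t) = 1 − (1 − p)^(t/21).
- Front-loaded hazard (Weibull, shape 0.5): risk(t) = 1 − (1 − p)^√(t/21).

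For p = 10% and constant hazard, 1 − 0.9^(14/21) = 6.8% and 1 − 0.9^(28/21) = 13.1%. The even-spread column averages risk(t) over the 15 possible visit days, t = 14 to 28.

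| Assumed hazard | Risk by day 21 | All seen day 14 | All seen day 28 | Visits spread evenly |
|---|---|---|---|---|
| Constant | 5% | 3.4% | 6.6% | 5.00% |
| Constant | 10% | 6.8% | 13.1% | 9.98% |
| Constant | 20% | 13.8% | 25.7% | 19.92% |
| Front-loaded | 10% | 8.2% | 11.5% | 9.94% |

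In 30 subjects, the 10% constant-hazard extremes are 30 × 0.0678 = 2.0 and 30 × 0.1311 = 3.9 expected subjects with an event. The front-loaded extremes are 2.5 and 3.4.

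**Chance that a given event is collected.** With visits spread evenly over the 15 days, an event on day d is captured with probability (29 − d)/15: 0.93 on day 15, 0.73 on day 18, 0.53 on day 21 and 0.07 on day 28. On average half of days 15 to 28 is observed.

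**The case against.** The strongest reply is that the window is symmetric, so early visits lower the percentage and late visits raise it by nearly the same amount. With visits spread evenly, the average is 9.98% against a true 10%, a difference of 0.02 percentage points. The extremes require every subject to be seen on the same edge of the window. Even then they differ by about two subjects in 30, while the exact 95% interval for 3 of 30 runs from 2.1% to 26.5%. The trial is single-arm, safety is descriptive (7.4.2), the endpoints do not define success (7.1), and the stopping rule in 10.2 is triggered by events and not by this percentage.

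Most of this stands. It limits the size of the problem and rules out any claim about type I error, power or a between-arm comparison. It does not supply a time horizon, and it does not change the fact that the same event is counted in one compliant subject and never collected in another.

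Two stronger readings are tempting, and the documents support neither:
- A reader might infer that the safety rate will be understated. That needs visits to skew early, and nothing in the documents suggests it.
- A reader might infer that the delayed bleeding named in 6.1 is what will be lost. Section 6.1 and Appendix 2 tie delayed bleeding to discharge or to the procedure and give no day, so nothing places it on days 15 to 28.

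It is also fair to object that the 14-to-28-day range depends on counting from the last procedure, which 4.2 contradicts. That conflict has to be settled first, but settling it would not fix the end of the window.

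**Conclusion.** The point holds as one of definition and ascertainment. Following the plan exactly gives 14 to 28 days of observation after the last procedure, a two-fold range, with no common cut-off and no allowance for time at risk. Whether a first related SAE on days 15 to 28 counts depends on the appointment date.

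The numerical effect is probably modest. Under an assumed 10% risk by day 21 and a constant hazard, 6.8% and 13.1% are outer limits, not expected results. Visits spread evenly give about 9.98%, and early clustering of events narrows the limits to 8.2% and 11.5%. Directional bias would need visits that skew early or late. All event rates, hazard shapes and visit distributions here are assumptions.

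Because the endpoint is descriptive with no success criterion, this does not threaten the trial. It is worth correcting because safety is the primary question and the correction is small.

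**What to change.** 1. Reconcile the start of the clock first. Section 4.2 counts from the first procedure, 5.4.2 and Appendix 1 from the last, and 7.4.2 does not say. Name one reference procedure in all of them.
2. In 4.3 and 7.4.2, define the endpoint by onset through one fixed day after that procedure, for example day 21, without a tolerance. Collection still starts at enrollment.
3. In 5.4.2 and 10.5, keep adverse event collection open to the cut-off for every subject. Add to Appendix 1 a telephone check on the cut-off day for anyone seen earlier. It should be listed as a planned contact, since 5.4.3 covers only unscheduled ones.
4. Report related SAEs with later onset beside the endpoint, so that no event counted under the present wording disappears.
5. Leave the 21 (±7) day visit and CT window unchanged. Narrowing it to +7/−0 would also fix the early end, but it would rule out CT scans on days 14 to 20, and that CT determines the clearance endpoint (5.5, 7.4.3).

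The cost is a brief call for subjects seen before the cut-off and a small protocol and CRF amendment, with IRB and FDA submission as appropriate (8.1, 9.9). The sample size is unaffected. With a common cut-off, the two-fold range in observation after the reference procedure falls to a ratio of 1.0 in subjects who complete follow-up. If the last procedure is the reference, differences in treatment length remain: from the index procedure, a day-21 cut-off gives 21 to 21 + 21 = 42 days. Follow-up duration should therefore be summarised with the percentage.
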